## 9. Intervention

Block randomization (blocks of six) will be performed with 1:1:1 random computer allocation of subjects into the three study arms. In the two inulin arms, chicory root-derived inulin (Cargill Inc., Wayzata, MN) will be diluted in 250 ml of sterile water and given at 8 or 16 g twice daily (**Figure 4**). The placebo arm will receive the same volume of sterile water twice daily, with the intervention given for 7 days or until death or hospital discharge. Prior studies suggest that these doses are likely to be safe and sufficient to confer benefit, even in the setting of critical illness. Subjects, investigators, and the treating ICU team will be blinded to the intervention arm, with blinding managed by the CUMC Research Pharmacy which will provide labeled, de-identified, semi-opaque fluid bags containing inulin/placebo in accordance with the U.S. Code of Federal Regulations governing labelling of new investigational drugs (21CFR 312.6). The intervention will be taken orally or given with enteric feeding by nursing staff overseen by the study team, with the first dose administered within 6 hours of ICU admission. The time course for the intervention and remaining study assessments is shown below in **Table 3**.

**Figure 4.** Chemical structure of inulin. Inulin is a naturally occurring polysaccharide derived from chicory root, agave, garlic, and other vegetable sources; it is a long chain carbohydrate of fructose polymers with  $\beta(1,2)$  glycosidic linkages which are indigestible by human enzymes but fermented by colonic anaerobic bacteria into short-chain fatty acids (chemical formula:  $C_{6n}H_{10n+2}O_{5n+1}$ ).

**Table 3.** Time course of intervention and main assessments during the study.

Type of Assessment	Inulin----->			Monitoring----->			
	Day 0	Day 3	Day 7	Day 14	Day 30	3 months	6 months
Rectal swab	X	X	X	X	X		
Whole stool	X	X	X	X	X		
Clinical data	X	X	X	X	X	X	X
Telephone follow-up						X	X

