### 10.3. Additional outcomes:

10.3.1. *Feasibility.* Descriptive demographic and clinical data will be compared across study groups to assess adequacy of randomization. Summary statistics (count data) will be recorded for patients across all 3 intervention arms to assess feasibility as (1) the enrollment rate (enrolled)/(enrolled+refusals) over each 12 month period; (2) protocol adherence (proportion of randomized subjects who receive 1 or more doses of the allocated intervention); and (3) fidelity of the intervention (defined as the proportion of high/low inulin allocated vs received and also categorically as receipt of 90% or more allocated doses of inulin across groups). Feasibility goals are as stated in Aim 1.

10.3.2. *Rates of pre-specified AEs.* There will be active ascertainment of AEs in the following categories, which will be compared between intervention groups. This will be done through the end of the intervention period (ICU Day 7) and also through Day 30/discharge to assess for delayed AEs.

- Stool frequency, measured by subject or nursing report by the number of spontaneous stools over the 24 hours preceding each assessment;
- Stool consistency, measured by subject or nursing report as an ordinal variable (0-4) over the 24 hours preceding each assessment;

- Abdominal bloating, measured by subject or nursing report as an ordinal variable (0-3) over the 24 hours preceding each assessment.
- Electrolyte abnormalities, measured by examining for differences in median values, minimum/maximum values, and proportions of values outside the normal range. This will be done for glucose, calcium, magnesium, phosphate, potassium, and sodium.
- Nausea, vomiting, obstruction, and abdominal pain. These will be recorded as present or absent based on bedside assessment of the subject or based on the nursing impression.
- Culture-proven infections, which will be considered both an AE and an outcome (see 10.3.4).

10.3.3. *Antibiotic resistance gene fraction on ICU Day 3.* DNA will be extracted from rectal swabs (MoBio PowerFecal, Carlsbad, CA) and assessed using multiplex quantitative PCR (Qiagen Cat. No. 330261, Valencia, CA) for 87 common antibiotic resistance genes. Within-individual differences in multiplex qPCR results will be compared from baseline to Day 3 both as summed changes and within relevant gene categories (e.g.,  $\beta$ -lactamase resistance genes) and compared between intervention groups.

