### 11.3. Exclusion criteria

- **Inability to receive oral or enteric fluids.** Patients will be excluded if they are *nil per os* or are unable to take fluid by mouth or delivered via enteric nasal or oral tube because they would be unable to receive the study intervention;
- **Inulin allergy.** Patients will be excluded for safety reasons if they have a known chicory allergy. Serious chicory allergies are exceedingly rare although mild respiratory symptoms and IgE-mediated food allergies have been reported;
- **Hyponatremia.** Patients will be excluded for hyponatremia with serum sodium  $\leq 128$  mEq/L because the intervention will be delivered in 500 ml of free water daily. If subjects develop hyponatremia (serum sodium serum sodium 125-128 mEq/L) after enrollment and randomization which persists at the time the subject is due to receive the study intervention, the study team will confer with the treating ICU team regarding whether the intervention should be deferred or further concentrated in order to minimize free water. If subjects develop severe hyponatremia (serum sodium serum sodium  $\leq 124$  mEq/L) after enrollment and randomization, the intervention will be withheld until 2 consecutive serum sodium values are within normal limits;
- **Immunosuppression.** Patients will be excluded if they have immunosuppression, as CD4 count  $< 200$  or absolute neutrophil count  $< 500$  or reasonable expectation of either during the study intervention period. We believe that the inulin works by modifying the gut bacteria. Excluding patients who lack the ability to mount an immune response improves trial homogeneity;
- **Surgery involving the intestinal lumen.** Patients will be excluded for surgeries involving the intestinal lumen within 30 days. The most common side effects from inulin are subjective bloating and abdominal distension. Although this bloating appears to be mild and self-limited, patients with recent bowel surgeries may be at greatest risk for such symptoms and will therefore be excluded;
- **DNR or DNI status.** Such patients have limited treatment goals and will be excluded to minimize heterogeneity;
- **No LAR.** Patients will be excluded if they lack capacity for consent and have no appropriate Legally Authorized Representative (LAR) to act as surrogate decision-maker.

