#### **15. Safety and adverse events (AEs)**

Adverse health events, laboratory irregularities, and even death are expected in ICU patients with sepsis and it would be difficult or impossible to accurately document and label all adverse health events. This is a common problem faced by ICU trials. The solution recommended by academic critical care research groups (e.g., Cook *et al.*) is to pre-specify AEs of interest for careful monitoring. In keeping with this approach, this study will produce detailed reports of these AEs for the DSMC at standard intervals while only unanticipated problems that also meet criteria for serious adverse events (SAEs) will be reported to the DSMC in real time. AEs will be reported for all individuals who have received one or more doses of the intervention. This study has pre-specified AEs in the following categories.

- Bloating: graded 0-3 based on patient report: patient mean and maximum values will be reported;
- Stool consistency and frequency: graded 0-4 for consistency and with an integer denoting frequency over 24 hours based on nursing report. For each patient, mean and maximum values will be reported;
- Electrolyte imbalances: For each patient, the minimum and maximum values for serum calcium, magnesium, phosphate, potassium, and sodium will be reported. This will be done for the 7 days of the intervention period and separately from Day 7 through Day 30/discharge;
- Gastrointestinal AEs: the gastrointestinal AEs of nausea, vomiting, bowel obstruction, and abdominal pain will be recorded as present or absent for each assessment and separated from other AEs to improve early pattern recognition by the DSMO;
- Infections: Infections are both an AE and an outcome and will be adjudicated as previously described. For each infection, the date of the infection, suspected site, organism, and antibiotics received will be recorded. Infections will be further classified as MDR vs non-MDR using the criteria previously described;
- Death: death will be gathered from the hospital EMR, which interfaces with the social security death index.

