## 17. Statistical methods

### 17.1. Overall plan for statistical analysis

After enrollment is complete, the REDCap dataset will undergo DCC cross-checks for quality and accuracy. The PI will review blinded data to identify errors which, if they exist, will be rectified by reference to paper CRFs or to the EMR. After quality checks are complete, the REDCap dataset will be closed and locked. The biostatistician will then perform an intent-to-treat analysis to determine the primary and secondary outcomes. The DSMO will have complete access both to the raw data and to the analytic code used by the biostatistician and will nominate a qualified monitor who will review this work for rigor. Once this is complete, the primary and secondary outcomes will be finalized. At this point, the locked data will be made available to the PI and other investigators for additional analyses. For all analyses,  $\alpha < 0.05$  will be considered statistically significant and two-sided testing will be performed. When death is a competing risk, Fine and Gray regression analyses will be performed.

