### 17.2. Determination of the primary and secondary outcomes

Primary outcome: within-individual change in relative abundance of SCFA producers. 16S rRNA gene sequencing data will be processed using the QIIME platform with appropriate rarification and filtering. The primary analysis will be intent-to-treat, restricted to the subjects who complete the Day 3 assessment and contribute data. Within-individual change in SCFA producers will be calculated as Day 3 minus baseline relative abundance and an ANOVA or Kruskal-Wallis (KW) test (if skewed data) will be used to assess for differences across the three groups. If there is no significant difference between the low- and high-dose inulin arms, these arms will be combined for comparison against placebo in the final analysis using a two-sample t-test or rank-sum test. Although the primary analysis will be with the Day 3 samples, unadjusted and adjusted longitudinal data analysis will be performed using the generalized estimating equation approach with working independence correlation structure.

Secondary outcome: MDRO colonization. Subjects who culture positive from rectal swabs from Day 3 for MRSA, VRE, or a Gram negative with non-susceptibility to a third generation cephalosporin will be classified as MDRO colonized and all other subjects as not MDRO colonized. The proportion of patients who are MDRO colonized on Day 3 will be compared between intervention groups using a chi-squared test or Fisher's test. For this analysis, patients in the inulin arms will be combined if testing shows no significant difference between these inulin arms. Because baseline colonization status is likely to be an important predictor of Day 3 colonization status, we will test whether baseline MDRO colonization rates differ between intervention groups. If such a difference is observed, we will reanalyze Day 3 MDRO colonization with stratification according to baseline MDRO colonization (baseline MDRO colonized vs not colonized). Exploratory analyses will examine Day 7 MDRO colonization status and semi-quantitative culture data using ANOVA or Kruskal-Wallis testing. The difference in rates of Day 3 MDRO colonization will be taken as the effect size estimate for future trials.

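### Section 10.3.2: the out-of-range electrolyte proportion is worded per laboratory value and does not separate low from high; define it per patient and by direction, and adjust post-dose sodium extremes for pre-dose sodium

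*Combined protocol and SAP*

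**What the plan says.** Section 10.3.2 introduces the pre-specified adverse events with "There will be active ascertainment of AEs in the following categories, which will be compared between intervention groups". For electrolytes it lists three measures: "Electrolyte abnormalities, measured by examining for differences in median values, minimum/maximum values, and proportions of values outside the normal range". It then names six analytes: "This will be done for glucose, calcium, magnesium, phosphate, potassium, and sodium".

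Section 15 gives a patient-level unit for one of the three measures: "For each patient, the minimum and maximum values for serum calcium, magnesium, phosphate, potassium, and sodium will be reported". Glucose is not in that list, and neither the median nor the out-of-range proportion is mentioned there.

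Section 17.1 sets the 0.05 level for all analyses and states that such results "will be considered statistically significant and two-sided testing will be performed". Section 17.2 names a method for repeated measurements, but under the primary outcome: "unadjusted and adjusted longitudinal data analysis will be performed using the generalized estimating equation approach". Section 17 contains nothing specific to the electrolyte comparison.

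On sodium, section 11.3 excludes patients at 128 mEq/L or below "because the intervention will be delivered in 500 ml of free water daily". It has the study team confer with the ICU team at 125-128 and withholds dosing at 124 or below. Section 9 says: "The placebo arm will receive the same volume of sterile water twice daily".

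**The concern.** Two features of the third measure are unsatisfactory.

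**Unit.** A proportion of values has the laboratory result as its denominator. Results come from routine care, the number per patient is not fixed, and values from one patient resemble each other. If they were pooled by arm and tested as independent, the test would reject too often when there is no arm effect, and patients with more draws would carry more weight.

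**Direction.** One out-of-range category mixes low and high. If an arm shifts downward, it gains low values and loses high ones, and the two changes partly cancel. Defining the measure per patient does not cure this.

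A smaller gap concerns glucose: because section 15 omits it, none of its three measures has a stated unit.

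What is at stake is how the safety report reads. The proportion could show an arm difference that only reflects repeated values, or show none beside a median and minimum that have moved. The sodium extremes are also compared without using each patient's pre-dose value, which gives up precision that the data already contain.

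**Working it through.** The plan states no power, rate or sample size for this outcome, so there is no figure to reproduce. It also gives no sodium distribution or number of draws. The figures below rest on these assumptions.

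**Inputs**
- From the plan: 102 expected enrolments (section 12, Retention), so 102/3 = 34 per arm; two-sided 0.05 (section 17.1).
- Assumed: normal range 135-145 mEq/L; sodium = patient mean + within-patient error, rounded to 1 mEq/L; between/within SD of 2/4, 3/3 or 4/3. Within-patient correlation = between² / (between² + within²): 4/20 = 0.2, 9/18 = 0.5, 16/25 = 0.64.

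**1. Pooled values, no arm effect.** Chi-squared test on values in three arms, 3,000 simulated trials per setting, means 136-140:

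| Values per patient | Rejection rate |
|---|---|
| 3 | 5.6-17.1% |
| 7 | 7.9-39.7% |
| 14 | 10.0-60.1% |

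Per-patient measures on the 7- and 14-value data (Kruskal-Wallis) reject in 4.0-5.7%.

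A second model agrees: beta-binomial, 30 v 30 patients, 30% of values out of range. With 7 values and intraclass correlation 0.5, the design effect is 1 + (7 − 1) × 0.5 = 4.0. The effective critical value is 1.96/√4 = 0.98, which gives a two-sided error of about 33%. The simulation gave 33.2%.

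**2. Why merging directions hides a shift.** Take SD 3/3, so total SD = √(9 + 9) = 4.24. With rounding, low means below 134.5 and high means above 145.5.
- Mean 141.5: low = Φ(−7/4.24) = 4.9%; high = 1 − Φ(4/4.24) = 17.3%; total 22.2%.
- Mean 138.5: low = Φ(−4/4.24) = 17.3%; high = 1 − Φ(7/4.24) = 4.9%; total 22.2%.

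Low values more than triple and the merged proportion does not move, because the two means sit symmetrically about 140. Further down the range the cancellation fades: at 138 the merged proportion is 20.5% + 3.9% = 24.3% (before rounding), and at 135 it is 45.3% + 0.7% = 46.0%.

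**3. Power, per-patient measures.** Both inulin arms v placebo (68 v 34), 7 values, correlation 0.5, rank-sum test:

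| Placebo mean to inulin mean | Either direction | Below range only |
|---|---|---|
| 141.5 to 138.5 | 5.6% | 91.5% |
| 141 to 138 | 9.8% | 92.6% |
| 140 to 137 | 44.1% | 95.3% |
| 139 to 136 | 79.8% | 97.6% |
| 138 to 135 | 93.0% | 97.9% |
| 137 to 134 | 96.9% | 98.2% |
| 141 to 139 | 5.0% | 55.6% |
| 140 to 138 | 11.7% | 62.4% |
| 138 to 136 | 56.7% | 74.0% |
| 137 to 135 | 67.5% | 75.0% |

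The planned minimum and median detect the 3 mEq/L falls in 97-99% of trials. For the 2 mEq/L falls the minimum detects 73-76% and the median 77-81%.

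**4. Adjusting for pre-dose sodium.** Same arms, placebo mean 138, entry sodium at least 129, 7 values, 2 mEq/L fall. A t-test on each patient's minimum is set against an analysis of covariance with the pre-dose value:

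| Correlation | Unadjusted | Adjusted |
|---|---|---|
| 0.2 | 83.3% | 86.3% |
| 0.5 | 78.0% | 91.8% |
| 0.64 | 57.7% | 85.6% |

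With no arm effect the adjusted analysis rejects in 5.0-5.4%.

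**The case against.** The strongest reply is that the inflated error rates belong to a test that the plan does not contain. A reader might infer that the trial will test pooled laboratory values as independent. The documents do not say so: section 10.3.2 speaks only of examining differences, section 15 uses patient-level summaries for electrolytes, and section 17.1 fixes the level and sidedness, not the unit. That stands. The error rates show what a literal reading would risk.

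A reader might also infer that a fall in sodium would go unseen. This is not supported either. The same sentence plans the median and the minimum, which detect the simulated falls at least about as well as a below-range proportion, so splitting the measure adds readability more than detection. Nor do the documents give a reason to expect an arm difference in sodium. The hazard they name is free water, and placebo receives the same volume, so water alone would not separate the arms. The near-total loss of power needs arm means on either side of mid-range; at a placebo mean of 138 or lower with a 3 mEq/L fall, the loss is small.

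Two further replies carry some weight. The plural wording does not strictly force low and high into one category. And section 15.2 refers to a data and safety monitoring plan, not available here, which might define the summaries for safety reporting. Neither supplies a unit or a direction in the document that defines the between-arm comparison.

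Finally, the covariate does not repair the wording of the proportion. That is true. It is a separate improvement to the sodium minimum and maximum and stands on its own gain in power.

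**Conclusion.** The point holds as a minor one, confined to one measure within one additional safety outcome. As worded, the out-of-range proportion has no patient-level unit and no split by direction. A pooled reading would be anti-conservative, and a per-patient reading that keeps both directions together can show nothing while the median and minimum in the same sentence show a shift. For glucose no measure has a stated unit.

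Under the assumptions above, pooled testing would reject in about 6-17%, 8-40% or 10-60% of null trials with 3, 7 or 14 values per patient. For a 3 mEq/L fall, merging directions costs anything from about 86 percentage points (91.5 − 5.6) to about 1 (98.2 − 96.9), depending on where the arm means lie. Covariate adjustment raises power for a 2 mEq/L fall from 57.7-83.3% to 85.6-91.8%. The documents supply no sodium distribution, so these figures show a range of possibilities and do not predict this trial's results.

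The primary and secondary results, the sample size, and the exclusion and dose-hold rules are unaffected.

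**What to change.** Amend section 10.3.2 as follows.

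1. Keep the median and the minimum/maximum, and state that each is calculated per patient for all six analytes, including glucose. Add glucose to the list in section 15.
2. Replace the out-of-range proportion with two per-patient measures after the first dose: the proportion of the patient's values below range and the proportion above range. Label any by-value proportion that is kept as descriptive.
3. Compare each patient's lowest and highest post-dose sodium between arms with the last pre-dose sodium as covariate.

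Optionally, report by arm the number and percentage of dosed patients who reach sodium 128 or below and 124 or below (the levels in section 11.3), with exact 95% confidence intervals and no test. These counts would be imprecise: 3/34 is 8.8%, with an exact interval of 1.9-23.7%.

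The cost is a few lines of wording, with no new data, visits or patients. The drawback is two proportions per analyte instead of one.
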